8.1 Adverse Event Definitions

The following are specific definitions of terms guided by the International Conference on Harmonization (ICH) Guidelines for Good Clinical Practice (GCP) and the U.S. Code of Federal Regulations that apply to this section:

Adverse Event: Any untoward medical occurrence in a subject or clinical investigation subject administered a pharmaceutical product and which does not necessarily have to have a causal relationship with this treatment. An AE is any unfavorable and unintended sign, symptom, or disease temporally associated with the use of an investigational medicinal product (IMP) or other protocolimposed intervention, regardless of attribution. This includes the following:

- AEs not previously observed in the subject that emerge during the protocol-specified AE reporting period, including signs or symptoms associated with ocular-graft-vs.-host disease (oGVHD) that were not present prior to the AE reporting period.
- Complications that occur as a result of protocol-mandated interventions.
- If applicable, AEs that occur prior to assignment of study treatment associated with medication washout, no treatment run-in, or other protocol-mandated intervention.
- Preexisting medical conditions (other than the condition being studied) judged by the investigator to have worsened in severity or frequency or changed in character during the protocol-specified AE reporting period

Subjects will be reminded to inform the study staff of any adverse effects that they have experienced or are experiencing after the first administration of study drug. In addition, subjects will record adverse

events in their diary throughout the study. All reports of adverse events during the study will be recorded on an Adverse Event Case Report Form (CRF). The subject should not be prompted about any adverse events that may occur during this trial.

All AEs and SAEs whether volunteered by the subject, discovered by study personnel during questioning, or detected through physical examination, laboratory test, or other means will be reported appropriately. For each adverse event, the following information will be recorded on the subject's Case Report Form(s): onset date, end date or continues, intensity, duration, relationship to test patch, action taken, and outcome. If a subject experiences a serious adverse event (SAE), study staff may discontinue the subject from study participation. The study staff must notify the IRB within 24 hours of receipt of the information. The study staff will instruct the subject to notify the research facility should any adverse event occur within 7 days of study completion. (For definitions of an AE and SAE, see below). Subjects who withdraw due to an adverse event may be replaced.

- Serious Adverse Event: An AE should be classified as an SAE if the following criteria are met:
 - 1. It results in death (i.e., the AE actually causes or leads to death.).
 - 2. It is life-threatening (i.e., the AE, in the view of the investigator, places the subject at immediate risk of death. It does not include an AE that, had it occurred in a more severe form, might have caused death.).
 - 3. It requires or prolongs inpatient hospitalization.
 - 4. It results in persistent or significant disability/incapacity (i.e., the AE results in substantial disruption of the subject's ability to conduct normal life functions).
 - 5. It results in a congenital anomaly/ birth defect in a neonate/infant born to a mother exposed to the investigational medicinal product (IMP).
 - 6. It is considered a significant medical event by the investigator based on medical judgement (e.g., my jeopardize the subject or may requires medical or surgical intervention to prevent any of the occurrences listed above.

To ensure consistency of AE and SAE causality assessments, the following general guideline will be applied:

Yes

There is a plausible temporal relationship between the onset of the AE and administration of the Pulmozyme, and the AE cannot be readily explained by the subject's clinical state, intercurrent illness, or concomitant therapies; and/or the AE follows a known pattern of response to the Pulmozyme; and/or the AE abates or resolves upon discontinuation of the Pulmozyme or dose reduction and, if applicable, reappears upon re-challenge

No

Evidence exists that the AE has an etiology other than the Pulmozyme (e.g., preexisting medical condition, underlying disease, intercurrent illness, or concomitant medication); and/or the AE has no plausible temporal relationship to Pulmozyme administration (e.g., cancer diagnosed 2 days after first dose of study drug)

• *Life-threatening:* Any adverse drug experience in which the subject was at risk of death at the time of the event. It does not refer to an event which hypothetically might have caused death if it were more severe.

Expected adverse event: Expected adverse events are those adverse events that are listed or characterized in the Package Insert (P.I) or current Investigator Brochure (I.B).

• *Unexpected adverse event:* Any adverse event, the specificity or severity of which is not consistent with the current Investigator's Brochure.

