The most likely discomforts a subject may experience by using rhDNase I administered as eye drops are eye burning or irritation, red watery eyes, or feeling like there is something in the eye. To see how subjects react to the study medication, their first dose will be given by the investigator in the clinic itself. Afterwards subjects will be asked to rate tolerability of the drug on the Visual Analogue Scale. Also, at each visit, subjects will be asked to complete the Visual Analogue Scale.

An allergic reaction to the drug cannot be predicted beforehand. In event of an allergic reaction, the drug will be stopped immediately, and symptoms will be managed appropriately depending on the severity of the reaction.

No single agent has yet been approved by the FDA for GVHD prevention or therapy.³⁴ Contact lenses, commonly used to treat oGVHD, will be withheld during the 14 day wash-out period and over the entire course of the study. Stopping contact lens wear may increase the subject's risk of worsening oGVHD. All study subjects will be encouraged to contact the research team immediately if they experience worsening of oGVHD.

No psychological, social, legal, or financial risk is expected from participating in the research.

There is always a risk of a loss of confidentiality.

2 Study Objectives

The objective of this study is to establish whether patients with ocular graft-vs.-host disease (oGVHD) are able to tolerate receiving rhDNase I 0.1% eye drops four times a day for eight weeks (primary tolerability objective) and to investigate the preliminary efficacy of rhDNase I 0.1% topical eye drop solution in treating oGVHD (primary efficacy objective).

3 Study Design

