3.2 Primary Study Endpoints

Primary Efficacy End Point: The primary end point is a mean reduction in corneal staining score after 8 weeks of treatment, as measured by Fluorescein and Lissamine dye staining.

Primary Tolerability End Point: The change in the test substance tolerance between Day 1 (post-dose) and at weeks 2, 4, 6 and 8.

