3.4 Safety Endpoints

Safety assessments include Vital Signs, recording of all complications and adverse events, as well as ophthalmic exam findings. All ocular and non-ocular adverse events will be assessed for severity and relationship to the investigational product.

Primary safety endpoint:

• The proportion of subjects at week 8 who were able to successfully complete a full eight weeks of therapy with topical administration four times per day (q.i.d.)

Secondary safety endpoint:

- All adverse events reported, whether deemed related to treatment, or not.
- Clinically significant changes in vital signs or ophthalmic examination from baseline.

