7.1 Sample Size Determination

The sample size is based on the primary efficacy end point (corneal RBS score) using the following assumptions: (i) mean RBS score in ocular GVHD population = 3.1, (ii) sigma (standard deviation) = 2.5, (iii) expected mean based on 60% effect = 1.24. These assumptions are based on our preliminary data in ocular GVHD patients where we found that treatment with DNase I eye drops reduced RBS score by 80% (mean).²⁵ A total of 30 subjects in each group will be required to detect the difference between groups using a 2-sided two-sample t test with an alpha level of 0.05 and 80% power. We elected to enroll 36 subjects per group.

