7.2 Statistical Methods

Biostatisticians from the Design and Analysis Core (DAC) of UIC-CCTS will perform the analysis. We will assess treatment efficacy based on the intent-to-treat principle using each participant's randomized treatment assignment to define treatment groups and outcomes. Safety variables will be analyzed with regard to treatment that participants actually received (the safety population). One eye (target eye) will be selected at screening visit for statistical comparisons as follows: (i) if only 1 eye meets inclusion criteria, this eye is used; (ii) if both eyes meet inclusion criteria, the eye with the higher RBS score is used; (iii) if both eyes have the same RBS score, then the one with the lower Schirmer I score is used; (iv) if both eyes have same scores, the right eye is used. Secondary analyses will be performed for the non-target eye as well. To assess the effect of treatment, we will compare each outcome measure between rhDNase I (study) vs. Vehicle (control) group over time using general linear mixed model, mixed-effects ordinal logistic regression, and mixed-effects multinomial logistic regression for continuous, ordinal and nominal variables respectively. Treatment, time and their interaction will be included in the model. Missing values of less than 25% will be imputed by using multiple imputations; otherwise will not be included in the analysis. Descriptive statistics will be utilized before the modeling to describe the sample. Assumptions behind each statistical method will be examined. Two-sided Pvalue less than 0.05 would be considered as statistical significance. All the analyses will be conducted by using SAS 9.2 (SAS Inst., Cary, NC).

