7.3 Subject Population(s) for Analysis

Subject population for analysis will include any subject enrolled in the study who received at least two weeks of treatment with study eye drops and attended at least the first post-treatment (week 2) follow up visit.

8 Safety and Adverse Events

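### Only adverse-event withdrawals may be replaced (section 8.1), the completion endpoint has no stated denominator, and section 7.3 leaves out the earliest withdrawals

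*Combined protocol and SAP*

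**What the plan says.** The replacement rule is one sentence in section 8.1: "Subjects who withdraw due to an adverse event may be replaced". It sets no limit and does not say who decides, which arm or randomisation number the new subject takes, or how the replaced subject is analysed. No other reason for withdrawal carries a replacement provision.

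Three measures bear on it:

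- Section 2 makes tolerating eight weeks of drops a primary objective.
- Section 3.2 defines the primary tolerability endpoint on the visual analogue scale (VAS): "The change in the test substance tolerance between Day 1 (post-dose) and at weeks 2, 4, 6 and 8".
- Section 3.4 defines the primary safety endpoint: "The proportion of subjects at week 8 who were able to successfully complete a full eight weeks of therapy with topical administration". It states no denominator. Under section 5.7, stopping study drug means withdrawal from the study.

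On who is analysed, section 7.2 says: "We will assess treatment efficacy based on the intent-to-treat principle", with safety analysed by treatment actually received. Section 7.3 then limits the analysis population to enrolled subjects who "received at least two weeks of treatment with study eye drops and attended at least the first post-treatment (week 2) follow up visit". Section 8.5.3 evaluates every exposed subject for adverse events. Section 4.4.2 asks those who withdraw before week 8 for the week 10 procedures and a tolerance rating.

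Section 7.1 requires 30 per group and adds: "We elected to enroll 36 subjects per group".

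**The concern.** The only loss that may be refilled is the loss that shows intolerance. Replacement after a house move or a missed visit would be largely neutral for tolerability. Replacement after an adverse-event withdrawal acts on subjects who have already failed the primary safety endpoint.

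Whether that does harm depends on who is counted, and the plan does not settle this for the completion proportion. Section 7.3 sharpens the problem. Section 1.5 names burning and irritation as the most likely discomforts. A subject who stops for these before the week 2 visit falls outside the section 7.3 population and may also be replaced. At stake is a completion figure that responds little to the withdrawals it is meant to measure, produced by a choice that could be made after the withdrawals are known.

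**Working it through.** **1. The plan's own figure.** Section 7.1 gives means of 3.1 and 1.24, SD 2.5, two-sided alpha 0.05 and power 80%. The difference is 3.1 − 1.24 = 1.86, or 1.86/2.5 = 0.744 SD. The normal approximation gives 29 per group. The t-test calculation gives 29.35, rounded up to the stated 30. Power is 80.9% at 30 per group and 87.6% at 36. The margin is 36 − 30 = 6 subjects, or 6/36 = 16.7%.

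**2. Completion under two denominators.** The documents give no withdrawal rates, so these are assumed: adverse-event withdrawal *a* of 5% to 20%, and other withdrawal 5%. True completion is *c* = 1 − *a* − 0.05.

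- All dosed subjects count: expected completion = *c*.
- Every adverse-event withdrawal is replaced and only the filled places count: expected completion = *c*/(1 − *a*).

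Filling 36 places takes 36/(1 − *a*) dosed subjects.

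| *a* | Dosed for 36 places | Adverse-event withdrawals | Completers | All dosed | Filled places |
|---|---|---|---|---|---|
| 5% | 37.9 | 1.9 | 34.1 | 90% | 0.90/0.95 = 94.7% |
| 10% | 40.0 | 4.0 | 34.0 | 85% | 0.85/0.90 = 94.4% |
| 15% | 42.4 | 6.4 | 33.9 | 80% | 0.80/0.85 = 94.1% |
| 20% | 45.0 | 9.0 | 33.8 | 75% | 0.75/0.80 = 93.8% |

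With all dosed subjects counted, replacement leaves the expected proportion correct. With filled places, a four-fold rise in adverse-event withdrawal moves the figure by less than one point.

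**3. Completion if section 7.3 sets the denominator.** Let *f* be the share of adverse-event withdrawals that come too early to meet section 7.3, and suppose other withdrawals come later. Completion becomes *c*/(1 − *f·a*). At *a* = 20%:

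- *f* = 0: 75%
- *f* = 0.5: 0.75/0.90 = 83.3%
- *f* = 1: 0.75/0.80 = 93.8%

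This effect needs no replacement at all, so deleting the sentence in section 8.1 would not remove it.

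**4. The passages side by side.** Section 7.2 (randomised assignment for efficacy, treatment received for safety), section 8.5.3 (all exposed subjects) and section 4.4.2 (tolerance rating sought after withdrawal) point to the all-dosed column. Section 7.3 points away from it for early withdrawals, but a subject who withdraws after attending week 2 still qualifies. No passage adopts the filled-places denominator, and none rules it out.

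**The case against.** The strongest reply is that replacing a subject is an enrolment matter. Enrolling an extra subject deletes nobody. The intent-to-treat statement, the by-treatment-received safety analysis and the evaluation of all exposed subjects all imply that withdrawn subjects stay. On that reading expected completion is undistorted, and the gap is one missing sentence about the denominator. Much of this stands, and several stronger readings that a reader might infer are not supported:

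- *Intolerant subjects are swapped out of the results.* No passage removes a replaced subject from analysis, and adverse-event records are kept for everyone exposed.
- *Replacement breaches intent-to-treat.* Adding subjects does not; dropping randomised subjects would. The text that sits badly with section 7.2 is section 7.3.
- *The arm with more harm is refilled more often.* This presumes that the replacement joins the same arm. Section 5.3 describes a list of 72 random numbers, each 1 or 2, with no entries set aside for replacements and no arm rule. Such a list does not guarantee 36 per arm, so a fixed number of places per arm is only a device for bounding the effect.
- *Completion is the primary tolerability endpoint.* It is the primary safety endpoint. The tolerability endpoint is the VAS change, for which no size is given here.
- *The six extra subjects are a built-in loss allowance.* Section 7.1 gives no reason for 36. Its calculation also uses the RBS score, whereas section 3.2 names fluorescein and lissamine staining, so the power figures reproduce section 7.1 without establishing power for the present endpoint.

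What remains is that the rule is written for adverse-event withdrawal alone, the denominator of a primary endpoint is open, and section 7.3 excludes the earliest withdrawals.

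**Conclusion.** The concern holds in a conditional form. The plan permits selective refilling of failures on the primary safety endpoint without fixing who is counted. If all dosed subjects count, the assumed rates give expected completion of 90% to 75% and no distortion. If only filled places count, they give 94.7% to 93.8%. If section 7.3 governs, the figure falls between these according to how many withdrawals come early. The documents lean towards the first case but do not settle it. All withdrawal rates, and the share coming early, are assumptions. The choice should be written down before withdrawals by arm are known.

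**What to change.** 1. Delete the replacement sentence in section 8.1. State that randomised subjects are not replaced, that all of them stay in the efficacy analysis, and that all dosed subjects stay in the VAS, safety and completion analyses.
2. In section 3.4, define the completion denominator as all dosed subjects, with adverse-event withdrawals counted as non-completers.
3. Amend section 7.3 so that it does not exclude early withdrawals from these analyses. Without this, the new wording would contradict it.
4. Optionally, name the six subjects per group above the required 30 as the allowance for losses, which the protocol does not now do.

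If replacement is kept, the minimum is a statement that replaced subjects stay in every analysis and every denominator.

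The cost is protocol wording. The downside is that if more than 6 of 36 in a group are lost, fewer than 30 have week 8 data. Keeping early withdrawals in the efficacy analysis also does not supply their staining scores: the week 10 procedures requested of them include no dye staining, so those values would fall under the missing-data rule in section 7.2.

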8.2 Classification of Adverse Events by Severity

All toxicities/adverse events will be graded according to the following definitions to code the intensity of the event.

Mild: Usually transient, requiring no special treatment, and does not interfere with the subject's daily activities.

Moderate: Traditionally introduces a low level of inconvenience or concern to the subject and may interfere with daily activities, but are usually relieved by simple therapeutic measures.

Severe: Causes an interruption of the subject's usual daily activity and traditionally required systemic drug therapy or other treatment.

Note: If the intensity of an adverse event changes, the event will be reentered as a separate event.

There is a distinction between the severity and the seriousness of an adverse event. Severity is a measurement of intensity; thus, a severe reaction is not necessarily a serious adverse event. For example, a headache may be severe in intensity, but would not be serious unless it met one of the criteria for serious adverse events listed previously.

8.3 Action(s) Taken

One or more of the following will be recorded by the Investigator for each adverse event:

- No action taken
- Discontinued study drug (Subject withdrawn due to this adverse event)
- Administered therapy
- Hospitalized subject (due to this adverse event)
- Other (specify) includes tests, labs confirming reaction

8.4 Outcome

The status of each adverse event will be recorded as follows, if applicable: SAE: Indicates that the adverse event met the criteria of a serious adverse event (SAE) and the SAE was reported to the IRB. Caused Withdrawal: Indicates that the adverse event caused the subject's withdrawal from the study.

8.5 PROCEDURES FOR ELICITING, RECORDING, AND REPORTING ADVERSE EVENTS

8.5.1 Eliciting Adverse Events

A consistent methodology for eliciting AEs at all subject evaluation time points will be adopted. Examples of non-directive questions include:

- "How have you felt since your last clinical visit?"
- "Have you had any new or changed health problems since you were last here?"

8.5.2 Specific Instructions for Recording Adverse Events

Investigators should use correct medical terminology/concepts when reporting AEs or SAEs. Avoid colloquialisms and abbreviations.

Page 35 of 47

a. Diagnosis vs. Signs and Symptoms

If known at the time of reporting, a diagnosis should be reported rather than individual signs and symptoms (e.g., record only liver failure or hepatitis rather than jaundice, asterixis, and elevated transaminases). However, if a constellation of signs and/or symptoms cannot be medically characterized as a single diagnosis or syndrome at the time of reporting, it is acceptable to report the information that is currently available. If a diagnosis is subsequently established, it should be reported as follow-up information.

b. Deaths

All deaths that occur during the protocol-specified AE reporting period (see Section I), regardless of attribution, will be reported to the appropriate parties. When recording a death, the event or condition that caused or contributed to the fatal outcome will be reported as the single medical concept. If the cause of death is unknown and cannot be ascertained at the time of reporting, report "Unexplained Death".

c. Preexisting Medical Conditions

A preexisting medical condition is one that is present at the start of the study. Such conditions will be reported as medical and surgical history. A preexisting medical condition should be re-assessed throughout the trial and reported as an AE or SAE only if the frequency, severity, or character of the condition worsens during the study. When reporting such events, it is important to convey the concept that the preexisting condition has changed by including applicable descriptors (e.g., "more frequent headaches").

d. Hospitalizations for Medical or Surgical Procedures

Any AE that results in hospitalization or prolonged hospitalization should be documented and reported as an SAE. If a subject is hospitalized to undergo a medical or surgical procedure as a result of an AE, the event responsible for the procedure, not the procedure itself, should be reported as the SAE. For example, if a subject is hospitalized to undergo coronary bypass surgery, record the heart condition that necessitated the bypass as the SAE.

Hospitalizations for the following reasons do not require reporting:

- Hospitalization or prolonged hospitalization for diagnostic or elective surgical procedures for preexisting conditions
- Hospitalization or prolonged hospitalization required to allow efficacy measurement for the study or
- Hospitalization or prolonged hospitalization for scheduled therapy of the target disease of the study.

e. Pregnancy

If a female subject becomes pregnant while receiving the study drug or within 30 days after the last dose of study drug, a report will be completed and expeditiously submitted to Genentech, Inc. Follow-up to obtain the outcome of the pregnancy will also occur. Abortion, whether accidental, therapeutic, or spontaneous, should always be classified as serious, and expeditiously reported as an SAE. Similarly, any congenital anomaly/birth defect in a child born to a female subject exposed to the {study drug} should be reported as an SAE.

Additional information on any Pulmozyme (rhDNase)-exposed pregnancy and infant will be requested by Roche Drug Safety at specific time points (i.e. after having received the initial report, at the end of the second trimester, 2 weeks after the expected date of delivery, and at 3, 6, and 12 months of the infant's life).

f. Post-Study Adverse Events

The investigator should expeditiously report any SAE occurring after a subject has completed or discontinued study participation if attributed to prior {study drug} exposure. If the investigator should become aware of the development of cancer or a congenital anomaly in a subsequently conceived offspring of a female subject who participated in the study, this should be reported as an SAE.

g. Reconciliation

The Sponsor agrees to conduct reconciliation for the product. Genentech and the Sponsor will agree to the reconciliation periodicity and format, but agree at minimum to exchange quarterly (no less frequently than monthly) line listings of cases received by the other party. If discrepancies are identified, the Sponsor and Genentech will cooperate in resolving the discrepancies. The responsible individuals for each party shall handle the matter on a case-by-case basis until satisfactory resolution. The sponsor shall receive reconciliation guidance documents within the 'Activation Package'.

